6.5.9 Principal Stratification

To reduce bias from possible treatment-dependent loss to follow-up due to death, intolerance, or other causes and possible treatment-dependent initiation of other disease-modifying treatments for ALS, the effect of treatment on ALSFRS-R and SVC will be estimated using the potential

outcome framework and principal stratification (Rubin 2006). We will estimate the visit-specific profile of average causal effects in the treatment- and visit-specific principal strata always survivors (i.e., the participants who would have lived to a given visit under both the active and placebo treatment exposures) and never initiators (i.e., the participants who would have not initiated another disease-modifying treatment for ALS prior to a given visit under both the active and placebo treatment exposure) in the FAS and ERO analysis sets. Time to loss to follow-up or initiation other disease-modifying treatments for ALS will be predicted from a conditional survival random forests model (Hothorn et al. 2006) using all baseline characteristics specified in Section 6.2 Baseline Characteristics.

6.5.10 Additional Sensitivity Analyses of Primary and Key Secondary Outcomes

Sensitivity analyses of primary and key secondary efficacy outcomes are as described in this R-SAP.

6.5.11 Subgroup Analyses

The following subgroups will be analyzed in the random-slopes model (see Section 6.5.4) for ALSFRS-R total score and SVC in the FAS by including subgroup, subgroup \times month, and subgroup \times treatment \times month terms:

- El Escorial definite or probable and less than 18 months since onset of weakness (both criteria vs. not both),
- Pre-baseline ALSFRS-R slope (high vs. low by median split),
- Baseline plasma NfL concentration (high vs. low by median split),
- Baseline TRICALS score (more negative vs. less negative by median split),
- Baseline use of riluzole by concomitant medication log (yes vs. no),
- Baseline use of edaravone by concomitant medication log (yes vs. no), and
- Baseline use of riluzole and edaravone (neither, riluzole only, edaravone only, both).

Conditional on findings from initial analyses, the following subgroups will also be analyzed:

- Age (less than 65 years vs. 65 years or older),
- Sex (female vs. male),
- Race (white vs. any minority race with greater than 5% prevalence in the sample),
- Ethnicity (Hispanic or Latino vs. non-Hispanic or Latino),
- BMI (less than 25 kg/m², 25 to less than 30 kg/m², 30 kg/m² or more),
- Chronic kidney disease (CKD) stage (stage 1 or better [eGFR 90 mL/min/1.73m² or more], stage 2 [eGFR 60 to 89 mL/min/1.73m²], stage 3 or worse [eGFR less than 60 mL/min/1.73m²]),
- Site (individual sites with at least 5 participants per treatment group and all participants from sites with fewer than 5 participants per treatment group pooled).

For each classification, unknown, not reported, and missing will be considered one group. All individuals not included in a specified subgroup will be combined into a mixed, "other" group.

The "other" group will be included in analyses if its prevalence is greater than 5%; otherwise, the "other" group will be excluded.

6.5.12 Comparison of Controls across Regimens

Comparisons of placebo participants across regimens are the same as specified in the M-SAP with baseline serum NfL level as an additional covariate in adjusted analyses plus applicable interaction terms as relevant to a given model.

6.5.13 Pharmacokinetic Analyses

Serum trehalose concentrations will be summarized by treatment group, time point (pre-dose and 1, 2, and 4 hours after SOI), and visit in the ERO sample. Concentrations below the limit of quantitation (BLQ) will be replaced with one half of the lower limit of quantitation. Summaries will include number of observations, number and percentage with concentrations BLQ, arithmetic mean, median, standard deviation, minimum, maximum, geometric mean, geometric coefficient of variation (calculated as sqrt(exp(variance of log-transformed concentrations) – 1)), and 95% confidence bounds for the geometric mean assuming log-normally distributed data.

Serum trehalose concentration data may be subjected to population pharmacokinetic analysis to derive population estimates of pharmacokinetic parameters and test the effect of various covariates such as age, weight, and sex. Details of the analysis will be described in a separate data analysis plan (DAP). This analysis may be performed by combining data from the current study with data from other studies of trehalose, if deemed appropriate. The population pharmacokinetic analysis will be performed by Seelos and reported in a separate modelling report.

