#### *1.3.2 Rationale for the Dose, Dosing Regimen, and Route of Administration*

**Error! Reference source not found.** If administered orally < 0.5% of ingested trehalose is absorbed into the blood stream. Therefore, to achieve therapeutic blood levels of trehalose, it is necessary to circumvent the metabolism in the human gastrointestinal tract. As such, Seelos has

developed SLS-005 an IV formulation of trehalose for injection, 90.5 mg/mL to be evaluated in this study.

In the single ascending dose study of IV trehalose in healthy subjects, the mean weight in the 54 g dose cohort was 74.5 kg. At the dose of 54 g, subjects received 0.72 g/kg. The area under the curve to time infinity ( $AUC_{inf}$ ) at that dose was  $8,595 \pm 2,575$  hour  $\times$   $\mu$ g/mL. Since clearance is dependent on body weight (i.e., clearance increases with increasing body weight), in order to achieve a consistent exposure in, at, or near the exposure at the MTD, 54 g/1 hour, a weight-based dose of 0.75 g/kg should achieve an exposure within the clinically acceptable safety range.

One of the proposed mechanisms of action of trehalose is to activate autophagy, the blockade of glucose receptors results in a starvation scenario within the cell (DeBosch 2016). Therefore, the MTD will be used to ensure significant exposure. Weekly dosing of IV trehalose is the only regimen to be evaluated in clinical trials to date (patients with OPMD and SCA3) and will be used in this trial.

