#### Study Drug Preparation

Trehalose Injection 90.5 mg/mL (an aqueous, sterile solution for IV infusion) is provided as a clear liquid in a 300 mL infusion bag containing 27.15 grams of trehalose. No preparation is required for administration of the study drug.

Placebo is also provided as a clear liquid in a 300 mL infusion bag. No preparation is required for administration of placebo.

The dose of IV trehalose or placebo will be calculated based on participant body weight to determine the volume administered to each participant. Each participant's weight should be measured consistently at each in-clinic visit. Shoes and heavy winter clothes (e.g. coats, sweaters, boots) should be removed prior to weighing. If shoes cannot be removed, then weight should be assessed with the participant's shoes on at each clinic visit. Doses are adjusted based on changes in body weight (2 kg increase or decrease) noted during clinical trial assessments. More than 1 bag may be needed per infusion based on the participant's body weight. The intended SLS-005 total infusion time, excluding interruptions, is 60 minutes for infusion volumes up to 2 bags (i.e. up to 600mL) and should not exceed 70 minutes. For patients who require more than 2 bags (i.e. >600mL) of study drug the intended SLS-005 total infusion time should be increased to 90 minutes and not exceed 100 minutes. Management of deviations/excursions is described in the Study Drug MOP.

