#### **5.4 Study Medication/Intervention, Administration, Escalation, and Duration**

The participant will receive weekly infusions of study drug (trehalose or placebo). Although for most participants the total infusion time of SLS-005 is set at 60 minutes (+ 10 minutes), participants who require more than 2 bags of study drug the infusion time should be increased to 90 minutes (+10 minutes) throughout the study. All infusions will be administered using an infusion pump and will be followed with an IV flush. The start calendar date and 24-hour clock time as well as the end calendar date and 24-hour clock time of each infusion will be recorded in the study database. If an infusion is interrupted due to infusion issues, i.e. loss of IV site, the infusion can be completed once access has been re-established unless > 30 minutes have elapsed. If 30 or more minutes have elapsed the infusion should not be restarted, and the volume infused prior to the interruption recorded in the CRF as the total dose administered.

If needed the use of an implanted venous access device (e.g. Mediport, PICC) or percutaneous indwelling catheter is permitted however small caliber indwelling catheters in peripheral vessels should only be inserted for single use. Participants are to be monitored for administration site reactions during study drug administration. Infusion site reactions or infusion reactions are to be recorded as AEs using the appropriate coding terms on the eCRF.

If needed, remote services such as infusions at home can be considered after the participant has completed at least 4 weeks of in-clinic infusions, as long as the participant has had no adverse reaction to the infusions and all safety assessments are within acceptable limits. Decision to permit home infusions is at the discretion of the site investigator. Participants approved by their site investigator for weekly infusions outside of the study site will still be required to attend on-site study visits at Week 16 (unless completed remotely due to pandemic-related or other reasons) and 24, and their associated IP infusions at these timepoints can be done in-clinic following completion of the study visit. Telephone visits at Weeks 2, 12 and 20 may be conducted in clinic if the participant is receiving their weekly infusions at the study site and the infusion will occur during the visit window.

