## 5.9 Overdose

Certain safety events that occur in association with investigational product may require reporting. These safety events include, but are not limited to, the following:

- Overdose of the investigational product, where ‘overdose’ is defined as  $> 125\%$  of the intended dose for a single treatment day infusion.
- Suspected abuse/misuse of the investigational product
- Inadvertent or accidental exposure to the investigational product
- Medication error involving study drug (with or without participant exposure to the investigational product, e.g., name confusion)
- The half-life of Trehalose Injection 90.5 mg/mL is approximately 1.5 hours, and there is no antidote. Trehalose is metabolized to 2 glucose molecules, there are no other metabolites. Supportive care with monitoring of vital signs, blood glucose levels, and liver enzymes should be considered. In 1 subject who received 81 g of Trehalose Injection 90.5 mg/mL, there was an increase in liver enzyme levels, but liver function remained normal and liver enzyme values returned to normal without treatment.

These safety events should be reported to the Coordination Center whether they result in an AE/SAE or not. Safety events associated with an AE/SAE should also be reported in the EDC. The SI should also contact the Medical Monitor within 24 hours of the SI’s awareness.

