### **8.2 Serum Pharmacokinetic Assessments**

Not all sites may have the capacity to collect PK for this regimen, therefore PK will only be collected on participants who are enrolled at a site capable of performing the PK collection procedures.

The first thirty-six (36) participants randomized within the regimen to reach the Week 8 visit at sites participating in the PK collection will complete the PK collection procedure. Any participant not able to complete Week 8 PK will be replaced.

Participants completing the PK collection will have blood collected for PK analysis at Baseline (Day 0) and Week 8 (Day 56) at the following time points: pre-dose and 1 hour  $\pm$  5 minutes, 2 hours  $\pm$  5 minutes, and 4 hours  $\pm$  5 minutes post start of infusion (SOI). At each time point, 4mL of blood will be collected.

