4.2 Pharmacokinetic Endpoints

The following pharmacokinetic endpoints will be evaluated:

• Serum trehalose concentration at the following time points: pre-dose, $60 (\pm 5)$ min after start of infusion (SOI), $120 (\pm 5)$ min after SOI, and $240 (\pm 5)$ min after SOI.

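### The 1-hour trehalose summary in SAP 6.5.13 pools 60- and 90-minute infusions, so it cannot be read as a peak or end-of-infusion level

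*SAP*

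**What the plan says.** - **PK summary (SAP 6.5.13).** Concentrations are "summarized by treatment group, time point (pre-dose and 1, 2, and 4 hours after SOI), and visit in the ERO sample". The statistics include the geometric mean, the geometric CV and log-normal confidence bounds for the geometric mean. There is no stratum for infusion duration, volume or weight. A population PK analysis is optional and left to a separate plan.
- **PK endpoint (SAP 4.2).** The only endpoint is concentration: "Serum trehalose concentration at the following time points: pre-dose", then 60, 120 and 240 minutes after the start of infusion. No Cmax or AUC is defined.
- **Infusion duration (protocol 5.3, Study Drug Preparation).** The intended time is "60 minutes for infusion volumes up to 2 bags (i.e. up to 600mL) and should not exceed 70 minutes". Above 600 mL, "the intended SLS-005 total infusion time should be increased to 90 minutes and not exceed 100 minutes". Protocol 5.4 repeats the rule: "participants who require more than 2 bags of study drug the infusion time should be increased to 90 minutes".
- **Sampling (protocol 8.2).** Everyone in the PK subset is sampled pre-dose and at 1, 2 and 4 hours (each ±5 minutes) from the start of infusion, at Baseline and Week 8. The subset is 36 participants. There is no separate schedule for the longer infusion.
- **Recorded times (protocol 5.4).** Start and end clock times of every infusion go into the database.

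**The concern.** One hour after the start, a 60-minute infusion is just finishing, while a 90-minute infusion has about 30 minutes to run. The planned table puts both samples in one cell under one time label. The resulting mean depends on the weight mix of the subset, its spread contains a component due only to infusion rate, and log-normal confidence bounds are computed on what may be a two-component mixture.

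The same issue can touch the comparison of visits. Volume follows body weight, so a participant whose weight crosses the cut between Baseline and Week 8 changes duration, and the 1-hour level moves with no change in clearance.

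What is at stake is the interpretation of a descriptive PK table. Since population PK is optional, this table could be the only PK result reported.

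**Working it through.** **Inputs from the documents.** Bag content 27.15 g per 300 mL and dose 0.75 g/kg (protocol 5.1). Upper screening weight 144 kg (4.2.2). Linear, dose-proportional kinetics from 27 to 81 g (1.2.3). Half-life: "The half-life of Trehalose Injection 90.5 mg/mL is approximately 1.5 hours" (5.9). AUCinf at 54 g of 8,595 ± 2,575, and "the mean weight in the 54 g dose cohort was 74.5 kg" (1.3.2).

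**Assumptions.** One-compartment model with constant-rate infusion; clearance and volume proportional to weight; durations exactly 60 and 90 minutes unless stated; share *p* of the active PK subset on 90 minutes, not given, taken as 10% to 90%; within-duration CV of 30%, borrowed from 2,575 / 8,595 = 0.30 by reading the ± as an SD.

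**1. The plan's own figure.** 300 mL × 90.5 mg/mL = 27.15 g, as stated.

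**2. Where the duration changes.** Two bags hold 54.3 g, and 54.3 / 0.75 = 72.4 kg. A weight of 74.5 kg, the mean of the 54 g cohort, needs 74.5 × 0.75 / 0.0905 = 617 mL, which is more than two bags. If weights were normal with mean 74.5 kg and an assumed SD of 12 to 18 kg, 55% to 57% would exceed the cut. Assumed means of 70 to 85 kg give 42% to 85%. Both groups are likely to be well represented.

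**3. Concentration by duration.** With k = ln 2 / 1.5 = 0.462 per hour and concentration in units of dose/volume:

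- during infusion: C(t) = (1 − e^(−kt)) / (kT)
- after infusion: C(t) = C(T) × e^(−k(t − T))

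| Time after start | 60 min | 90 min | Ratio 90/60 |
|---|---|---|---|
| 1 h | 0.801 | 0.534 | 0.667 |
| 2 h | 0.504 | 0.573 | 1.135 |
| 4 h | 0.200 | 0.227 | 1.135 |

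The 1-hour ratio is 60/90 whatever the half-life, because both infusions are still running up to that moment and only the rate differs. Over the permitted durations it runs from 60/100 = 0.60 to 70/90 = 0.78. The 2- and 4-hour ratio is 1.10 to 1.22 for half-lives of 2 to 1 hours. Within a 90-minute infusion, the 1-hour level is 0.534 / 0.721 = 74% of that infusion's own end level.

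**4. Pooled 1-hour geometric mean, relative to the 60-minute value.** This is 0.667^p: 0.96 at p = 0.1, 0.82 at p = 0.5, 0.69 at p = 0.9. The shortfall is 4% to 31%.

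**5. Pooled geometric CV.** Log-variance = ln(1 + 0.30²) + p(1 − p) × [ln(ratio)]², and CV = √(exp(variance) − 1), the SAP's own formula.

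- 1 h, p = 0.5: 0.0862 + 0.25 × 0.1644 = 0.1273, so CV = 36.8%.
- 1 h, p = 0.25 or 0.75: 35.2%. At p = 0.1 or 0.9: 32.6%.
- 2 h and 4 h, p = 0.5: 0.0862 + 0.25 × 0.0160 = 0.0902, so CV = 30.7%.

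Splitting by duration returns the 1-hour CV to the assumed 30% in each stratum.

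**The case against.** The strongest reply is that the table is correct as labelled. It reports concentrations at times after the start of infusion, derives no Cmax or AUC, and nowhere calls the 1-hour value a peak. A reader might infer that the summary misstates exposure. The documents do not support that: under the linear kinetics they report, AUC does not depend on infusion duration, and the error arises only when the 1-hour mean is read as something it is not labelled to be. This stands.

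A reader might also infer that the table would show heavier participants as under-exposed and so undermine the weight-based dose. That does not follow either. The planned summary has no split by weight, the dose rationale in protocol 1.3.2 rests on AUC from an earlier single-dose study, and the protocol's objectives and endpoints contain no PK item.

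The size is uncertain too. Protocol 5.4 says 60 minutes applies to most participants, which points to a share below one half, while the 74.5 kg cohort mean points the other way. The 30% CV comes from AUC in six healthy subjects on a fixed dose. For these reasons a range is shown.

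Finally, the remedy is imperfect. A split at 600 mL is itself a split by weight, and its 1-hour contrast of about 0.67 needs a note that infusion rate explains it. A permitted 70-minute infusion sampled at 60 minutes is still running, at 60/70 = 0.86 of the 60-minute level, so the shorter stratum is not perfectly clean. These points limit the benefit but do not justify pooling the two durations at 1 hour.

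**Conclusion.** The point holds as a limited one about a descriptive analysis. The 1-hour cell combines two different phases of infusion whose levels differ by a factor of about 0.67 (0.60 to 0.78 over the permitted durations), so its pooled mean is neither a peak nor an end-of-infusion level. The 4% to 31% shortfall and the rise in CV from 30% to about 33% to 37% rest on the one-compartment model, weight-proportional clearance and volume, exact durations, and assumed values for the share and the base CV.

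The effect on spread is essentially confined to 1 hour. At 2 and 4 hours the CV changes by less than one point and the pooled geometric mean lies 1% to 12% above the 60-minute value. Total exposure and efficacy inference are unaffected, and nothing here bears on whether the dose or the infusion times are right.

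**What to change.** In SAP 6.5.13, state that concentration summaries, at least at 1 hour, will be presented separately by planned infusion duration (60 minutes for up to 600 mL, 90 minutes above), with a footnote that the 1-hour sample in the longer infusion is taken before its end. Add a listing of actual sample time relative to the recorded end of infusion. A listing suits this better than a summary by time from end, because the 1-hour sample in a 90-minute infusion has a negative time and the two groups share no common point.

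No new data are needed, and sampling and dosing stay as they are. The cost is precision: if 3:1 holds in the subset, 36 × 0.75 = 27 active participants are divided into two cells, about 13 or 14 each if the split is even and fewer in one if it is not.

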6.5.14 Pharmacodynamic Biomarker Analyses

Change in LC3-II levels in CSF will be summarized by treatment group and visit in the ERO. Summary statistics will be provided for the values, change from baseline, and percent change from baseline at each scheduled assessment time point. The effect of treatment on pharmacodynamic response will be estimated in the repeated-measure model (see Section 6.5.3). Pearson and Spearman correlations between change in LC3-II levels in the CSF and concurrent change in ALSFRS-R total scores and SVC percent-predicted will be estimated among participants with complete data.

6.6 Safety Analyses

6.6.1 Treatment-emergent Adverse Events

Summaries and analyses of treatment-emergent adverse events (TEAE) are the same as specified in the M-SAP with the following revisions.

TEAEs are defined as those adverse events with onset dates in the interval from treatment initiation to either the Final Safety Visit if completed, the date of death if the participant dies, 28 days after last study contact if the participant early terminates or is lost to follow-up, or the date of first dose of study drug during participation in the OLE, if so exposed. The interval is inclusive except for adverse events that occur on the day of treatment initiation and are known to precede first exposure to study drug.

In addition to summaries specified in the M-SAP, TEAEs will be summarized by Medical Dictionary for Regulatory Activities (MedDRA) system organ class and preferred term for fatal

TEAEs, TEAEs that occurred during a participant's COVID-19 infection (defined as 5 days prior to symptom onset to end of COVID-19 symptoms or end of double-blind follow-up, if ongoing), and TEAEs and serious TEAEs stratified by the following subgroups: baseline riluzole use, baseline edaravone use, age, sex, race, ethnicity, weight, BMI, and CKD stage. Subgroup classifications will be the same as described in Section 6.5.12 Subgroup Analyses except that the "other" group will be retained regardless of prevalence.

Treatment-dependent differences in the proportion of participants experiencing a given type of TEAE will not be tested.

6.6.2 Safety Labs

Summaries and analyses of clinical safety labs are the same as specified in the M-SAP with the revision that lab results collected more than 28 days after last dose of study drug will not be tabulated, that abnormal levels will be classified to a toxicity grade based on quantitative grading using National Cancer Institute (NCI) Common Terminology Criteria for Adverse Events (CTCAE) version 5.0, and with the addition that maximum toxicity over all post-baseline visits that occur within 28 days or fewer after last dose of study drug will be included in shift tables along with visit-specific shifts.

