- 5 During each infusion, vital signs associated with the infusion (systolic and diastolic pressure, respiratory rate, and heart rate) are to be measured pre-infusion, 30 minutes ( $\pm 5$  mins) after the start of infusion (SOI), 60 minutes after the start of infusion ( $\pm 10$  mins), and 90 minutes ( $\pm 10$  mins) after the start of infusion. If a participant requires a 90-minute infusion duration due to receiving more than 2 bags of study drug an additional vital signs measurement is to be completed approximately 30 minutes ( $\pm 10$  mins) after the end of the 90-minute infusion.
- 6 Clinical safety labs include hematology (CBC with differential), complete chemistry panel, thyroid function and urinalysis. Hb A1C will be included in labs at baseline, week 16 and week 24. Serum pregnancy testing will occur in women of child-bearing potential at the Master Protocol Screening Visit and as necessary during the study. Pregnancy testing is only repeated as applicable if there is a concern for pregnancy.
- 7 Adverse events that occur after signing the master protocol consent form will be recorded.
- 8 The DNA sample can be collected after the Baseline Visit if a baseline sample is not obtained or the sample is not usable.
- 9 Administer first dose of study drug only after Baseline Visit procedures are completed.
- 10 Participants will only have a Follow-Up Safety Call at this time if they *do not* continue on in the OLE. Participants who continue into OLE will have a Follow-Up Safety Call after their last dose of investigational product during the OLE period.
- 11 Vital status, defined as a determination of date of death or death equivalent or date last known alive, will be determined for each randomized participant at the end of the placebo-controlled portion of their follow-up (generally the Week 24 visit, as indicated). If at that time the participant is alive, his or her vital status should be determined again at the time of the last patient last visit (LPLV) of the placebo-controlled portion of a given regimen. We may also ascertain vital status at later time points by using publicly available data sources as described in section 8.15 of the Master Protocol.
- 12 If the CSF collection is unable to be performed for logistical reasons, such as scheduling, at the Week 16 Visit, it may be performed at the Week 24 Visit.

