### **6.9 Process for Early Terminations**

Participants who early terminate from the study and do not complete the protocol per ITT will be asked to be seen for an in-person Early Termination Visit and complete a Follow-Up Safety Call.

The in-person Early Termination Visit should be scheduled as soon as possible after a participant early terminates. If the participant early terminates during the placebo-controlled portion of the Regimen, all assessments that are collected at the Week 24 in-clinic visit should be conducted. The Follow-Up Safety Call should be completed approximately 28 days after the last dose of study drug.

If the Early Termination Visit occurs approximately 28±3 days after the last dose of study drug, the information for the Follow-Up Safety Call can be collected during the Early Termination Visit, and a separate Follow-Up Safety Call does not need to be completed. If the in-person Early Termination Visit does not occur within 28±3 days of the last dose of study drug, the Follow-Up Safety Call should occur approximately 28 days after the last dose of study drug and the Early Termination Visit will be completed after the Follow-Up Safety Call.

If a participant decides to discontinue study drug, but will complete the protocol per ITT, an in-person Early Termination Visit and Follow-Up Safety Call is not necessary.

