#### *6.10.12 Process for Early Terminations from the OLE*

Participants who early terminate from the study be asked to be seen for an in-person Early Termination Visit and complete a Follow-Up Safety Call.

The in-person Early Termination Visit should be scheduled as soon as possible after a participant early terminates. If the participant early terminates during the OLE period, all assessments that are collected at the OLE Week 52 in-clinic visit should be conducted. The Follow-Up Safety Call should be completed approximately 28 days after the last dose of investigational product.

If the Early Termination Visit occurs approximately 28±3 days after the last dose of investigational product, the information for the Follow-Up Safety Call can be collected during the Early Termination Visit, and a separate Follow-Up Safety Call does not need to be completed. If the in-person Early Termination Visit does not occur within 28±3 days of the last dose of investigational product, the Follow-Up Safety Call should occur approximately 28 days after the last dose of investigational product and the Early Termination Visit will be completed after the Follow-Up Safety Call.

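### SAP 6.6.2 leaves labs taken more than 28 days after last dose out of its tables, although RSA 6.9 permits Early Termination Visit labs on days 29–31 and later

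*SAP*

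**What the plan says.** **SAP 6.6.2 (Safety Labs).** As a stated revision of the Master SAP, "lab results collected more than 28 days after last dose of study drug will not be tabulated". The worst-grade shift is likewise restricted to "maximum toxicity over all post-baseline visits that occur within 28 days or fewer after last dose of study drug".

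**RSA 6.9 (Process for Early Terminations).** The content of the ET Visit is set by reference to Week 24: "all assessments that are collected at the Week 24 in-clinic visit should be conducted". RSA 6.7 shows that this includes safety labs with HbA1c. Three sentences govern timing:

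- The default: "The in-person Early Termination Visit should be scheduled as soon as possible after a participant early terminates".
- The merger with the safety call: "If the Early Termination Visit occurs approximately 28±3 days after the last dose of study drug", the call's content can be collected at the visit.
- Otherwise, when the visit is not within 28±3 days, the call takes place at about day 28 and the "Early Termination Visit will be completed after the Follow-Up Safety Call".

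No latest day is given. RSA 6.10.12 repeats the arrangement for the open-label extension (OLE): "the Early Termination Visit will be completed after the Follow-Up Safety Call". RSA 6.9 also says that a participant who stops drug but completes follow-up needs no ET Visit.

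**Related rules.** SAP 6.1 keeps observations made after permanent discontinuation in the Safety Full (STF) set when the participant remains on study. SAP 6.6.1 lets the treatment-emergent adverse event (TEAE) interval for someone who terminates early run to 28 days after last study contact. For HbA1c, the Schedule of Activities says "Hb A1C will be included in labs at baseline, week 16 and week 24".

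**The concern.** The RSA has sites draw a full set of labs at a visit that may fall after day 28, and the SAP then keeps those results out of its lab tables. SAP section 1 does not resolve this. It makes the RSA authoritative on conduct and the R-SAP authoritative on safety analysis, so both rules operate as written.

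The affected results come from people who stopped early, where tolerability problems are most likely to be found. HbA1c is the sharpest case. Someone who terminates before Week 16 and is seen after day 28 has no post-baseline HbA1c in the tables, for a drug that RSA 5.9 says is metabolised to glucose. Liver tests matter too: RSA 5.11.1 describes one serious event of raised liver enzymes, considered possibly related.

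The lab and adverse event rules also start from different points, last dose and last study contact. An event based on a late ET lab can therefore count as a TEAE while the lab value behind it is absent from the 6.6.2 tables.

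**Working it through.** The plan states no figure to reproduce. The check compares windows.

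**1. ET Visit against the lab cut-off** (days after last dose; inputs from RSA 6.9 and SAP 6.6.2)

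- Merger window: 28 − 3 = 25 to 28 + 3 = 31, which is 7 days.
- Tabulated: days 25, 26, 27 and 28. Not tabulated: days 29, 30 and 31, or 3 of 7.
- Visits through day 28: always tabulated.
- Visits after day 31: never tabulated, and the RSA sets no upper limit.

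**2. Participants who stop drug but stay on study** (nominal lab visits on days 56, 112 and 168, from the Schedule of Activities)

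Days since last dose = visit day − last-dose day. The result is kept if this is 28 or less.

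| Last dose | Week 8 | Week 16 | Week 24 |
|---|---|---|---|
| Day 28 | 28, kept | 84, out | 140, out |
| Day 56 | 0, kept | 56, out | 112, out |
| Day 84 | – | 28, kept | 84, out |
| Day 112 | – | 0, kept | 56, out |
| Day 140 | – | – | 28, kept |

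Week 24 labs on day 168 are kept only if the last dose was on day 140 or later (168 − 28). Post-baseline HbA1c is scheduled only at Weeks 16 and 24, so a last dose before day 84 (112 − 28) removes both values from the tables. The STF set nominally includes these observations.

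**3. RSA timing sentences side by side**

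The last sentence depends on what it means for the visit not to occur within 28±3 days.

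- Read as outside days 25–31: a visit that could take place on day 10 is sent to after the call, which contradicts the default.
- Read as not done by day 31: there is no contradiction for early visits, but a visit deferred under this rule falls after day 31 and is never tabulated.

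**4. Number affected**

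The documents give neither an early-termination rate nor the timing of ET Visits. Both are assumptions here. RSA 4.1 gives N = 160. Number = 160 × share terminating early × share of those seen after day 28.

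- Low: 160 × 0.05 × 0.10 = 0.8, about 1.
- Middle: 160 × 0.15 × 0.25 = 6.
- High: 160 × 0.30 × 0.50 = 24.

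These counts cover ET labs only. The off-drug participants in step 2 come on top and cannot be counted from the documents.

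**The case against.** The strongest reply is that the 28-day limit is a deliberate on-treatment window. It is written as a revision of the Master SAP and repeated for maximum toxicity. RSA 5.9 gives a half-life of about 1.5 hours, so day 28 is 28 × 24 / 1.5 = 448 half-lives after dosing. Keeping off-drug values out of a worst-grade shift is defensible. That stands, and it is why later labs belong in a separate table. It does not explain a boundary inside the RSA's own visit window, because day 31 is 31 × 24 / 1.5 = 496 half-lives and pharmacology does not separate the two days.

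Second, most ET Visits may well be prompt. Under RSA 5.7 infusions are a week ± 3 days apart, so someone who leaves while dosing on schedule is at most about 10 days from the last dose, and a prompt visit is tabulated. This also stands. It limits the size of the gap but does not close it.

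Third, glucose and liver tests are also drawn at Weeks 4 and 8, and abnormalities recorded as adverse events can still reach the TEAE tables. That is true, but HbA1c has no such earlier sample.

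Four stronger readings are tempting, and the documents do not support them:

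- That the labs are discarded. The SAP only declines to tabulate them. Listings may be specified in the Master SAP, which is not among the documents.
- That early terminators as a group lose their final labs. Only those seen after day 28 do.
- That day 31 is the deadline for the ET Visit. It is the last day for merging the visit with the call.
- That 3/7 of ET Visits are lost. That would need visits spread evenly over days 25–31 and none earlier.

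**Conclusion.** The concern holds as a misalignment between the SAP's lab cut-off and the RSA's visit rules. It is not an arithmetic error, and it does not touch the primary efficacy analysis. Labs from compliant ET Visits on days 29–31 or later, and labs more than 28 days after last dose from participants who remain on study off drug, are left out of the lab tables and the maximum-toxicity shift. The STF definition and the TEAE interval are both wider. That the exclusion follows from the text is certain. How many people it affects is not: the range of about 1 to 24 for ET labs rests wholly on the assumed 5–30% early termination and 10–50% late visits. The conflict within RSA 6.9 and 6.10.12 depends on a literal reading of the 28±3-day condition, but the wording permits that reading and sites need a single rule.

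**What to change.** **SAP 6.6.2.** Extend the on-treatment lab cut-off from 28 to 31 days after last dose, for both the tabulations and the maximum-toxicity shift, to match the RSA's 28±3-day window. This alone is not enough. A visit placed after the call because it missed the window falls beyond day 31, and the TEAE interval is tied to last contact, so a day-31 limit does not match it either. Labs beyond the cut-off should therefore go into a separate, flagged off-treatment tabulation, kept out of the on-treatment maximum-toxicity shift. It should cover both late ET Visit labs and the labs of off-drug participants still in follow-up, so that the two groups are treated alike.

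**RSA 6.9 and 6.10.12.** The sentence asking for a prompt ET Visit and the sentence placing it after the safety call conflict for a visit that could occur before day 25. The passages must be reconciled. Which timing rule applies is for the sponsor to decide.

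**Cost.** One extra table, a changed date filter and a wording clarification in the next RSA amendment. No additional visits or samples are needed.
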